6.3.1. Non-Responder Imputation (NRI)

For analysis of categorical efficacy and health outcomes variables, missing data will be imputed using an NRI method. Patients will be considered non-responders for the NRI analysis if they do not meet the categorical efficacy criteria or have missing clinical efficacy data at a time point of interest.

The NRI method may be used when the estimand of interest uses the composite strategy (FDA 2021) for handling intercurrent events. In this strategy, patients with any intercurrent events that lead to the permanent discontinuation of assigned study treatment are defined to have failed treatment for all subsequent time points.

In addition, patients who were not adequately assessed to determine if they meet the clinical requirements for response at the time point of interest are also considered to have failed treatment.

For any interim analyses that occur, patients who, based on their treatment start date, would not have completed the visit corresponding to the selected endpoint at the time of the database lock will not be included in the analysis of that endpoint. Patients who have discontinued or otherwise have missing data and would have otherwise completed that visit at the time of database lock will be counted as non-responders for the interim analysis.

6.3.2. Modified Baseline Observation Carried Forward (mBOCF)

For patients discontinuing investigational product due to an AE, the baseline observation for the endpoint will be carried forward to the corresponding visit for all missing observations after the patient discontinued study treatment. For patients discontinuing investigational product for any other reason, the last nonmissing postbaseline observation before discontinuation will be carried forward to the corresponding visit for all missing observations after the patient discontinued. For all patients with sporadically missing observations prior to discontinuation, the last nonmissing observation before the sporadically missing observation will be carried forward to the corresponding visit. Randomized patients without at least 1 postbaseline observation will not be included for evaluation with the exception of patients discontinuing study treatment due to an AE.

The mBOCF method is based on an estimand that handles the intercurrent event of discontinuing study drug due to an AE by defining the patient as not receiving any benefit from study drug after the event. That is, the patient is defined as reverting back to baseline regardless of any continuing efficacy benefits they may still have received after the event. For other intercurrent events (eg, discontinuation due to reasons other than an AE) or sporadic missingness the "while on treatment" strategy is applied. That is, the endpoint is defined as the last observed value at or before the visit of interest before the patient discontinued study treatment.

For any interim analyses that occur, patients who, based on their treatment start date, would not have completed the visit corresponding to the selected endpoint at the time of the database lock will not be included in the analysis of that endpoint. Patients who have discontinued or otherwise have missing data and would have otherwise completed that visit at the time of database lock will be treated using mBOCF for the interim analysis.

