8.1. Discontinuation from Study Drug

8.1.1. Permanent Discontinuation from Study Drug

Study drug may be permanently discontinued during the study. Patients who discontinue study drug early will undergo early termination procedures, which include an ETV and post-treatment follow-up visits.

The investigator will also complete any AE reporting and follow-up that may be required (if applicable, see Section 9.2).

If a patient's study drug is discontinued before the end of the study, the patient should complete the ETV and post-treatment follow-up period as follows:

- Patients who discontinue investigational product during [redacted] will return for post-treatment follow-up visits (Visits 801 and 802) [redacted] after the end-of-treatment visit.
- Patients who discontinue study drug [redacted] will return for post-treatment follow-up visits (Visits 801 and 802) [redacted] after the end-of-treatment visit.

[figure not shown]
Possible reasons leading to permanent discontinuation of investigational product include the following (list is not exhaustive):

Patient Decision

- The patient or the patient's designee, for example, parents or legal guardian, requests to discontinue investigational product.

[redacted]

[redacted]

Disease Worsening

- The patient requires rescue therapy for exacerbation of UC at doses higher than those specified in the “dose stabilization” inclusion criterion (for example, prednisone **CCI** Inclusion Criterion [9]), or with medications specified in the “prohibited medications” exclusion criterion (for example, IV corticosteroids, infliximab, or IV cyclosporine; Exclusion Criterion [19]) (see also [Appendix 5](#)).

Safety Criteria for Study Drug Discontinuation

- The patient has a diagnosis of any of the following during the study:
 - Cancer other than squamous cell or basal cell carcinoma of the skin
 - Polypoid or non-polypoid dysplasia that is endoscopically visible or invisible
 - Active TB (see Section [9.4.5.2](#))
 - HIV/AIDS
 - Hepatitis B or development of detectable HBV DNA (see Section [9.4.5.4](#))
 - Hepatitis C or development of detectable HCV RNA (see Section [9.4.5.5](#)).
- The patient requires a colectomy during the study.
- The patient has a systemic hypersensitivity event or anaphylaxis to mirikizumab (Section [7.8.3.2](#)). Study drug should be discontinued after a systemic hypersensitivity event or anaphylaxis.

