- The patient becomes pregnant. Pregnant patients **will not** undergo an endoscopy/flexible sigmoidoscopy at the ETV.
- The patient has absolute lymphocyte count **CCI** after retesting (see Section [8.1.2](#)).
- The patient is non-compliant with LTBI treatment (see Section [9.4.5.2](#)).
- The patient experiences an AE or SAE that, in the opinion of the investigator or sponsor, would preclude him/her from continuing to receive study drug or if they experience disease worsening that requires rescue therapy with protocol excluded medications.

Other Reasons for Study Drug Discontinuation

- The investigator determines that the patient is repeatedly noncompliant with study procedures and/or study drug (see Section [7.6](#)).
- Inadvertent enrollment (see Section [8.1.3](#)).

Patients discontinuing from the investigational product prematurely for any reason should complete AE and other follow-up procedures per Section 2 (Schedule of Activities), Section 9.2 (Adverse Events), and Section 9.4 (Safety).

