6.3. Handling of Dropouts or Missing Data

Intercurrent events (FDA 2021) are events which occur after the treatment initiation and make it impossible to measure a variable or influence how it should be interpreted. Examples of such

events include treatment discontinuation due to death or adverse events (AEs), rescue treatment, and loss to follow-up. The missing data methods described below handle intercurrent events in different ways and thus are relevant to different estimands.

The Schedule of Activities outlined in the protocol specifies the allowable windows for assessments. Assessments performed outside these windows will not be excluded from any analysis, but will be reported as a protocol deviation (see Section 6.15). While every effort will be made to reduce missing data, the missing data imputation method of NRI will be used when patients are permanently discontinued from study drug or otherwise have missing data. For the "as observed" analysis, only data from completers at the visit are relevant, and therefore the analysis does not need to deal with missing data.

For any interim analyses that occur, patients who, based on their treatment start date, would not have completed the visit corresponding to the selected endpoint at the time of the database lock will not be included in the analysis of that endpoint unless otherwise specified. Patients who have discontinued or otherwise have missing data and would have otherwise completed that visit at the time of database lock will be counted as non-responders for the interim analysis. For example, if a patient who discontinued at Week 12 of the study would have been in Week 24 of the study at the time of database lock, would not be included in the analysis of endpoints at Week 36 or Week 52. If that same patient who discontinued would have been at Week 48 at the time of the interim database lock if they had remained in the study, they would be counted as a non responder for Week 36, but not included in the Week 52 analysis.

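### SAP 6.3.2 carries baseline forward after an adverse-event stop only where data are missing, but its own estimand sets every later visit to baseline, and nothing says how observed post-stop values are handled

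*SAP*

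**What the plan says.** SAP 6.3.2 gives an operational rule and then the estimand it is meant to serve.

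- **AE stop, rule:** "the baseline observation for the endpoint will be carried forward to the corresponding visit for all missing observations after the patient discontinued study treatment".
- **AE stop, estimand:** "the patient is defined as reverting back to baseline regardless of any continuing efficacy benefits they may still have received after the event".
- **Other stops, rule:** the last postbaseline value before discontinuation is "carried forward to the corresponding visit for all missing observations after the patient discontinued".
- **Other stops, estimand (while on treatment):** "the endpoint is defined as the last observed value at or before the visit of interest before the patient discontinued study treatment".

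Protocol 8.1.1 provides for measurement after the stop: "Patients who discontinue study drug early will undergo early termination procedures, which include an ETV and post-treatment follow-up visits". The same section exempts pregnant patients from having to "undergo an endoscopy/flexible sigmoidoscopy at the ETV", which implies that other patients have that endoscopy.

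SAP Tables AMBU.6.5 and AMBU.6.6 specify mBOCF, alongside an as-observed summary, for change from baseline in:

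- PUCAI and abdominal pain (secondary table);
- SF, RB, total symptomatic score, ES, CRP, fecal calprotectin, PGRS and nocturnal stool (exploratory table).

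**The concern.** The rule acts only on gaps in the data. The estimand acts on the event, and makes the patient's change zero after an AE stop even if a value was recorded. A programmer who follows the rule keeps a recorded post-stop value. A programmer who follows the estimand overwrites it. Both can claim to follow 6.3.2, and they can report different means.

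The stake is whether the mBOCF means describe the quantity the SAP says they describe. SAP 6.3.2 also applies mBOCF at interim analyses. The planned interim in 6.16.2 summarises MMS component scores and PUCAI scores when about 15 patients of 40 kg or less reach Week 12. With groups this small, one patient is visible in a mean.

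**Working it through.** **Step 1. Where rule and estimand part (AE stops).**

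| Value at a visit after the stop | Change under the rule | Change under the estimand |
|---|---|---|
| Missing | 0 | 0 |
| Observed and assigned to that visit, change d | d | 0 |

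They differ only in the second row. For other stops the pattern is the same: an observed post-stop value is kept by the rule, while the estimand uses the last value before discontinuation.

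**Step 2. Can the second row occur?**

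- *Are post-stop data collected?* Yes. Protocol 8.1.1 requires an early termination visit (ETV) and follow-up visits, with endoscopy at the ETV unless the patient is pregnant. Most of the relevant Schedule of Activities rows are redacted, so the other measurements taken there cannot be listed.
- *Is there a written route into an analysis visit?* One, and for diary items only. SAP Appendix 1 falls back on an imputed visit date at the centre of the visit window when no actual date exists, so diary entries made after the stop could form a weekly score. The device is marked for collection at Visit 16 and in the next column, whose label is redacted. I read that column as the ETV, which is an assumption.
- *Is there a rule that assigns ETV or follow-up values to Week 12, 24, 36 or 52?* None found. The diary table in Appendix 1 lists no ETV row.
- *Is there a rule that sets post-stop values to missing or to baseline before mBOCF?* None found.

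The second row is therefore possible and unregulated. Its frequency is unknown.

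**Step 3. Size if it occurs.** The documents give no figure to reproduce. If k patients keep a change d instead of 0 in a group of n:

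shift in mean = k × d / n

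Group sizes come from SAP 5.2: about 10 patients above 40 kg, about 20 at 40 kg or below, about 30 in all. The split of the 20 between the two mg/kg doses is not stated. The values of d and k are assumptions. For PUCAI with k = 1:

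| d | n = 10 | n = 20 | n = 30 |
|---|---|---|---|
| -10 | -1.0 | -0.5 | -0.33 |
| -20 | -2.0 | -1.0 | -0.67 |
| -35 | -3.5 | -1.75 | -1.17 |

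With k = 2 these double. A worsening of +20 at n = 10 gives +20/10 = +2.0, so the direction is not fixed. For ES, d = -1 at n = 10 gives -0.1.

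Worked case: nine patients average -30, and the tenth stopped for an AE with a recorded post-stop change of -20.

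- Rule: (9 × (-30) + (-20)) / 10 = -29.0
- Estimand: (9 × (-30) + 0) / 10 = -27.0

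The 2-point gap is one tenth of the 20-point reduction that defines a PUCAI response.

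**The case against.** The strongest reply is that the mismatch may never bite. A patient who stops drug leaves the treatment schedule, and the mBOCF analyses are at fixed weeks or scheduled visits. If ETV and follow-up values are never assigned to those visits, the scheduled value is missing and rule and estimand give the same answer. This stands as a limit on the consequence. It does not settle the text, because the SAP does not say that such values stay unassigned.

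Three stronger readings are tempting and are not supported:

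- *That post-stop values do remain in the means.* A reader might point to SAP 6.3: "Assessments performed outside these windows will not be excluded from any analysis". That sentence concerns visit windows, with breaches reported as protocol deviations. It does not turn an ETV into a Week 12 or Week 52 assessment.
- *That NRI shows how mBOCF should have been written.* In 6.3.1, patients whose intercurrent event ends assigned treatment permanently "are defined to have failed treatment for all subsequent time points", and 6.3 makes discontinuation a trigger for NRI in its own right. But 6.3.1 also pairs a missing-data sentence with a defining sentence, and one could let the defining sentence govern in 6.3.2 too.
- *That an NRI failure who contributes an improved mBOCF change is a fault in itself.* For stops other than AEs this is intended, because a composite and a while-on-treatment strategy answer different questions. Only for AE stops would it signal the mismatch.

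The objection on importance also holds. The documents give no expected AE-stop rate, Protocol 3.2.4 reports few such stops in the adult Phase 2 study, and no treatment comparisons are planned. Of the visible mBOCF variables, only abdominal pain change appears in the SAP's table of secondary objectives.

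**Conclusion.** SAP 6.3.2 contradicts itself on AE stops: the rule is conditional on missingness and the estimand is not. The parallel gap exists for other stops. No other part of either document resolves it.

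The consequence is conditional. Any post-stop value that enters an analysis visit would be kept under the rule and would shift the mean by d/n per patient, upward or downward. The figures above rest on assumed values of d and k and on approximate group sizes, and the number of affected values cannot be determined from the documents. The effect is confined to descriptive secondary and exploratory change-from-baseline summaries. The primary PK endpoint is untouched. Severity: minor.

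**What to change.** In SAP 6.3.2:

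1. **AE stops.** Carry baseline forward to all visits after the discontinuation date, whether or not a value was observed. Setting all post-discontinuation values to missing before mBOCF is applied has the same effect.
2. **Observed post-stop values.** Show them in a listing only. The as-observed summaries are not the place, because SAP 6.3 restricts them to completers at the visit.
3. **Other stops.** State whether an ETV value counts as the last value before discontinuation, so that the rule matches the while-on-treatment estimand. This choice has a price. A patient who stops before Week 12 may have the ETV endoscopy as the only postbaseline endoscopic score. If it is excluded, 6.3.2 drops that patient from the ES summary, since its exception covers AE stops only.
4. **Definitions.** Say which date is the discontinuation date, and whether ETV and follow-up values are ever assigned to an analysis visit.

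The cost is a few sentences in the SAP and one flag in the analysis dataset, with no new data. The mBOCF means could move either way or not at all.

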9.2. Adverse Events

Investigators are responsible for monitoring the safety of patients who have entered this study and for alerting Lilly or its designee to any event that seems unusual, even if this event may be considered an unanticipated benefit to the patient.

The investigator is responsible for the appropriate medical care of patients during the study.

Investigators must document their review of each laboratory safety report.

The investigator remains responsible for following, through an appropriate health care option, AEs that are serious or otherwise medically important, considered related to the investigational product or the study, or that caused the patient to discontinue the investigational product before completing the study. The patient should be followed until the event resolves, stabilizes with appropriate diagnostic evaluation, or is reasonably explained. The frequency of follow-up evaluations of the AE is left to the discretion of the investigator. The investigator will record all relevant AE/SAE information in the eCRF.

Lack of drug effect is not an AE in clinical studies, because the purpose of the clinical study is to establish treatment effect.

After the ICF is signed, study site personnel will record via eCRF the occurrence and nature of each patient's preexisting conditions, including clinically significant signs and symptoms of the

disease under treatment in the study. In addition, site personnel will record any change in the condition(s) and any new conditions as AEs. Investigators should record their assessment of the potential relatedness of each AE to protocol procedure or investigational product, via eCRF.

The investigator will interpret and document whether or not an AE has a reasonable possibility of being related to study drug, study device, or a study procedure, taking into account the disease, concomitant treatment, or pathologies.

A “reasonable possibility” means that there is a cause and effect relationship between the investigational product, study device and/or study procedure and the AE. The investigator answers yes/no when making this assessment.

Planned surgeries and nonsurgical interventions should not be reported as AEs unless the underlying medical condition has worsened during the course of the study.

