4.3. Exploratory Objectives

Table AMBU.4.3. Exploratory Objectives and Endpoints

Objectives	Endpoints
Exploratory	
To summarize the change in baseline in biomarkers To evaluate the time to symptomatic response	Change from baseline in fecal calprotectin Change from baseline in C-reactive protein CCI
To evaluate the time to symptomatic remission	Time to symptomatic remission (defined as $SF = 0$, or $SF = 1$ with a ≥ 1 -point decrease from baseline, and $RB = 0$)
To summarize the change from baseline of individual MMS subscores and the composite symptomatic subscore over time in patients receiving mirikizumab	The numerical value and change from baseline in each of the following items: SF (at each visit) RB (at each visit) ES (Weeks 12 and 52) The composite clinical endpoint of the sum of the SF and RB subscores (at each visit)
CCI	CCI
CCI	CCI

Abbreviations: ES = Endoscopic subscore; MMS = Modified Mayo Score; NRS = numeric rating scale; PGIC = Patient's Global Impression of Change; PGRS = Patient's Global Rating of Severity; RB = rectal bleeding; SF = stool frequency; UC = ulcerative colitis.

5. Study Design

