6.1.1. Analysis Populations

Patient populations are defined in Table AMBU.6.1 along with the analysis they will be used to conduct. Patients will be analyzed according to the weight/treatment dose group to which they were assigned for all populations, found in Table AMBU.6.2.

Table AMBU.6.1. Definition of Population

Population	Description
Efficacy and Health Outcomes	
Modified Intent-to-Treat (mITT) Population	All enrolled patients that received at least 1 dose of treatment, even if the patient does not receive the correct dose, or otherwise does not follow the protocol. Patients will be analyzed according to the treatment to which they were assigned. Unless otherwise noted, efficacy and health outcomes analyses will be conducted on this population.
Safetya	All patients who received at least 1 dose of the study drug. Patients will be
Salety	analyzed according to the weight/treatment dose group to which they were assigned.
Pharmacokinetics	
PK evaluable	All patients who received at least 1 dose of investigational product and have
	sufficient blood sampling to allow for PK evaluation.

Abbreviation: PK = pharmacokinetic.

Table AMBU.6.2. Weight/Treatment Dose Groups for Each Analysis Study Period and Population

Study Period	Analysis Population	Weight/Treatment Dose Groups
Induction Period	mITT; Safety	≤40 kg 5mg/kg miri IV; ≤40 kg 10mg/kg miri IV; >40 kg 300mg miri IV; All miri
Induction and Maintenance Periods	mITT; Safety	≤40 kg 5mg/kg miri IV; ≤40 kg 10mg/kg miri IV; >40 kg 300mg miri IV; All miri
Maintenance Period	mITT	≤20 kg 50mg miri SC >20 kg and ≤ 40 kg 100mg miri SC >40 kg 200 mg miri SC; ≤20 kg NR 10mg/kg miri IV & 50mg miri SC >20 kg and ≤ 40 kg NR 10mg/kg miri IV & 100mg miri SC >40 kg NR 300mg miri IV & 200 mg miri SC; All miri

Abbreviations: IV = intravenous; mITT = modified intent-to-treat; miri = mirikizumab; NR = non-responder (at Week 12); SC = subcutaneous.

The weight/treatment dose groups shown in Table AMBU.6.2 reference the specific treatment regimens to which pediatric patients are assigned at Week 0 (for the induction period) and at Week 12 (for the maintenance period) and are dependent on the participants' weight at those respective visits and their clinical response status at Week 12 for the maintenance period as

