Abbreviations: CFB change from baseline; CI = confidence interval; mBOCF = modified baseline observation carried forward; mITT = modified intent-to-treat; MMS = Modified Mayo Score; NRI = non-responder imputation; NRS = Numerical Rating Scale; PUCAI = Pediatric Ulcerative Colitis Activity Index; Q12W = every 12 weeks.

 Table AMBU.6.6.
 Description of Exploratory Efficacy/Health Outcomes Analyses

Measure	Variable	Analysis Method (Section 6.1.3)	Population (Section 6.1.1)	Time Point(s)
Mayo Score and components	Change from baseline in SF, RB, and Total Symptomatic Score	Descriptive statistics and 95% CI for mean with mBOCF and as observed.	mITT	At each scheduled visit
	Change from baseline in ES	Descriptive statistics and 95% CI for mean with mBOCF and as observed.	mITT	Weeks 12 and 52
	Time to first symptomatic response	Descriptive statistics and 95% CI for mean.	mITT	During Induction Period
	Time to first symptomatic remission	Descriptive statistics and 95% CI for mean.	mITT	During Induction Period
	MMS Alternative Clinical Remission	Proportion for each weight/treatment dose group along with the 95% 2-sided CI with NRI and as observed.	mITT	Weeks 12 and 52
CRP	CRP CFB	Descriptive statistics and 95% CI for mean with mBOCF and as observed.	mITT	Week 12 Week 52
Fecal calprotectin	Fecal calprotectin CFB	Descriptive statistics and 95% CI for mean with mBOCF and as observed.	mITT	Week 12 Week 52
PGIC	Mean PGIC Score	Descriptive statistics and 95% CI for mean as observed.	mITT	Week 4, Week 8, Week 12, and Week 52
PGRS	PGRS Score CFB	Descriptive statistics and 95% CI for mean with mBOCF and as observed.	mITT	At each scheduled visit.
Nocturnal Stool	Nocturnal Stool Score CFB	Descriptive statistics and 95% CI for mean with mBOCF and as observed.	mITT - In patients with a nocturnal stool score ≥1 at baseline	At each scheduled visit.
CCI				At each scheduled visit.
Bristol Stool Scale	Loose stool	Proportion for each weight/treatment dose group along with the 95% 2-sided CI with NRI and as observed	mITT, in patients with loose stool at baseline	At each scheduled visit.

		Analysis Method	Population	
Measure	Variable	(Section 6.1.3)	(Section 6.1.1)	Time Point(s)
EIMs	Resolution of Baseline EIMs	Proportion for each weight/treatment dose group along with the 95% 2-sided CI with NRI and as	mITT – in patients with EIMs at baseline	Weeks 12 and 52
		observed.		

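### For change in ES, the mBOCF rule can drop children who stop early for a non-AE reason and have no usable postbaseline score, while children who stop for an AE are kept at zero change

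*SAP*

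**What the plan says.** SAP 6.3.2 treats stops differently according to the reason.

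- AE stops: "For patients discontinuing investigational product due to an AE, the baseline observation for the endpoint will be carried forward", so the change is zero.
- Stops for any other reason: "the last nonmissing postbaseline observation before discontinuation will be carried forward to the corresponding visit".
- No postbaseline value: "patients without at least 1 postbaseline observation will not be included for evaluation with the exception of patients discontinuing study treatment due to an AE". That sentence has randomized patients as its subject, although Protocol 7.2 describes an open-label study with assignment by weight.

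Lack of efficacy falls under the other reasons, because Protocol 9.2 says "Lack of drug effect is not an AE in clinical studies".

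SAP Table AMBU.6.6 lists "Change from baseline in ES" as an exploratory variable at Weeks 12 and 52 in the mITT population, summarised as "Descriptive statistics and 95% CI for mean with mBOCF and as observed". Table AMBU.6.1 defines mITT as "All enrolled patients that received at least 1 dose of treatment, even if the patient does not receive the correct dose".

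The first scheduled postbaseline endoscopy in the protocol's Schedule of Activities is at Visit 6, which SAP Appendix 1 identifies as Week 12.

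**The concern.** Two children may both stop at Week 8 with no usable endoscopy after baseline. If one stopped for an AE, that child enters the Week 12 mean at zero change. If the other stopped because the drug was not working, that child is left out. Inclusion then depends on the reason for stopping, and that reason can be related to the outcome. For the second child the mBOCF row is no different from the as-observed row beside it, and the mITT label no longer describes who was analysed.

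The SAP handles the same child differently elsewhere. Endoscopic remission and ES = 0 (Table AMBU.6.5) use NRI, which under SAP 6.3.1 counts missing data as failure. Two summaries of the same endoscopy, both labelled mITT, could therefore rest on different children.

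At stake is a descriptive mean in small groups. SAP 6.16.2 also lists the MMS component scores at Week 12, of which ES is one, among the summaries at the interim analysis used to confirm the dose for children of 40 kg or less.

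**Working it through.** The documents give no mean ES change, no standard deviation and no rate of stopping before Week 12. There is thus no planned figure to reproduce, and only the direction and scale can be examined.

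**Inputs**
- n: about 10 children above 40 kg and about 20 at 40 kg or less (SAP 5.2). The split of the 20 between the 5 and 10 mg/kg groups is not stated.
- k: children with no usable postbaseline ES who stopped for a non-AE reason. Not given; varied below.
- m: mean change in the retained children. Assumed −1.0 point for illustration.
- c: mean change assigned to the excluded children. Zero in the main illustration, as for AE stops.

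**Formula**

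Mean with everyone counted = [(n − k) × m + k × c] / n. With c = 0 this is m × (n − k)/n. The retained-only mean m then overstates it by n/(n − k) − 1, whatever the value of m.

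**Results with m = −1.0 and c = 0**

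| n | k | Mean, all counted | Mean, retained only | Overstatement |
|---|---|---|---|---|
| 10 | 1 | −0.90 | −1.00 | 10/9 − 1 = 11% |
| 10 | 2 | −0.80 | −1.00 | 10/8 − 1 = 25% |
| 20 | 1 | −0.95 | −1.00 | 20/19 − 1 = 5% |
| 20 | 2 | −0.90 | −1.00 | 20/18 − 1 = 11% |

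**Sensitivity to c** (n = 10, k = 1, m = −1.0)
- c = −1: (−9 − 1)/10 = −1.00, no bias.
- c = 0: (−9 + 0)/10 = −0.90.
- c = +1: (−9 + 1)/10 = −0.80.

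There is overstatement only if the excluded children did worse than those retained.

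**Can k be above zero?** Three provisions bear on this.
1. Early stoppers go to an ETV (Protocol 8.1.1). Only pregnancy stops are stated to be exempt from endoscopy there (Protocol 8.1.1 and 9.1.2), so most other early stoppers should have an ETV score.
2. SAP 6.3 keeps assessments made outside their windows, but does not assign an ETV endoscopy to Week 12. For non-AE stops, SAP 6.3.2 carries forward only values from before discontinuation, and the ETV follows the stop. A child whose only later score is at the ETV has a postbaseline observation but perhaps no value eligible to be carried forward.
3. Children who withdraw from the study are asked for AE and other safety follow-up (Protocol 8.2), and some may be lost to follow-up (Protocol 8.3). Either may have no ETV endoscopy.

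So k could be zero if ETV scores are obtained and used. It is above zero for any child with no ETV endoscopy, or whose ETV score is ruled out.

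**The case against.** The strongest objection is the ETV. A reader might infer that every child who stops early for lack of efficacy disappears from the mean. The documents do not support that. A child who needs a prohibited UC medication must stop study drug and complete an ETV (Protocol 7.7), and endoscopy there appears to be the norm. Such a child would usually have a postbaseline ES. This stands as a limit on size. It does not close the gap, because the SAP neither says that the score counts nor names its visit.

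The analysis is also minor: exploratory and descriptive, in a trial whose primary objective is PK, with the secondary endoscopic endpoints protected by NRI. SAP 6.2 plans no treatment comparisons, so it would be wrong to say that dose groups are formally compared on this mean. This stands too.

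Finally, SAP 6.3.2 declares a while-on-treatment strategy for non-AE stops, and a child with no on-treatment score arguably has no value under it; setting the change to zero would then be a preference. Yet the same paragraph defines the endpoint as the latest value seen up to the visit while still on drug. Read literally, a child with only a baseline score has change zero. The exclusion sentence departs from that wording, and the repair agrees with it.

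**Conclusion.** The point holds as a conditional one. The mBOCF rule makes inclusion of a child without a usable postbaseline ES depend on why study drug was stopped, and it departs from the mITT label and from the NRI handling of the same child. Mean ES improvement can be overstated if those excluded did worse than those retained, which is plausible for lack-of-efficacy stops but not shown for others, such as a family's decision.

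The illustrative size is 11% for 1 of 10 and 5% for 1 of 20, assuming zero change in the excluded child, and it falls toward zero if ETV endoscopies are counted.

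Two further inferences are not supported:
- A reader might take the 30 enrolled for 25 evaluable as the expected loss and obtain 30/25 − 1 = 20%. That allowance concerns PK evaluability (SAP 5.2), not endoscopy before Week 12.
- A reader might extend the point to CRP, fecal calprotectin or PUCAI. Their collection schedule is redacted, so the first postbaseline value cannot be established.

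The reference to randomized patients is a wording error and is not evidence of bias.

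**What to change.** Replace the exclusion sentence in SAP 6.3.2 with:

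*mITT patients with a baseline value but no usable postbaseline observation who have discontinued study drug for any reason will have the baseline value carried forward (change = 0).*

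In the same section:
- State whether an ETV endoscopy counts as a postbaseline observation and to which visit it maps. If it counts, the child keeps that score and the zero-change rule applies only where there is none.
- Use mITT in place of *Randomized*. The new sentence does this.
- Report, per dose group, the number of patients with no usable postbaseline value, with the reasons for stopping.
- Keep the as-observed row, so that the effect of the imputation can be seen.

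The cost is one sentence, one mapping rule, a small programming change and a short count table. The downside is that mean changes may be slightly less favourable, and that zero change is itself an assumption for children who stopped for reasons unrelated to efficacy.
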